# Interventions

CBT for Loneliness (CBT-L): CBT is effective for treating a wide variety of disorders. 45-48 The mechanism behind CBT's efficacy comes from its ability to change an individual's beliefs/thoughts, which serves to change behavior (in the case of the current study, increasing meaningful social interactions and reducing opioid use). 46,49-53 CBT has been shown to be efficacious in both computer and telephone formats, 54-56 as well as when administered by individuals other than highly trained mental health professionals. 57-59 Additionally, CBT was chosen over other formats such (e.g., social skills training, enhanced social support) because CBT has shown the strongest effects in reducing loneliness. 60 CBT-L is a brief, patient-centered, tailored, one-on-one, 6-session intervention. Each weekly session is ~45 minutes via telehealth. We will use Cully and Teten's Brief Cognitive Behavioral Therapy manual (see CBT-L Appendix) which was originally designed for specificity to a limited number of topics to reduce the number of CBT sessions to 6. This CBT protocol was developed to be adaptive in terms of treatment length and topic areas and is helpful for targeting symptoms or lifestyles that are not part of a formal diagnosis (e.g., loneliness). CBT-L seeks to improve emotional functioning and enact behavior change through addressing maladaptive thinking and behaviors in 6 sessions:

Page 5 of 20

- Session 1: Case history (e.g., onset of feeling alone, when was it most prominent, what has worked well before; severity and impact of feeling lonely), review CBT model, identify maladaptive thoughts
- O Session 2: Identifying and changing maladaptive thoughts
- o Session 3: Identifying and changing maladaptive thoughts
- o Session 4: Behavioral activation and exposure
- o Session 5: Behavioral activation and exposure
- Session 6: Problem solving and relapse prevention

Participants will use a four-step process for identifying and addressing maladaptive thoughts by discussing: (1) their stated beliefs, (2) whether the belief is 100% true, (3) alternative beliefs, and (4) whether anything could change the accuracy of the belief (i.e., how realistic is this belief). For example, if a participant states "No one wants me at my mom's birthday party because my drug use has hurt them," they would be asked to estimate the accuracy of this belief (0-100%) and to dispute it. For example, the original belief may be altered to "They wouldn't have asked me if they didn't want me there," "I love my mom and she would appreciate it," or "It's uncomfortable being at these events because of my drug use, but it's important to be with connected for my recovery." Similarly, the therapist will focus on correcting myths affecting interpersonal engagement to help the participants understand that many negative beliefs about being lonely and feeling like a burden are inaccurate. 62 Behavioral activation is used to increase the participant's activity level to improve mood. Loneliness contributes to avoidance thereby limiting use of adaptive coping strategies and reinforcing loneliness and negative affect. By increasing one's activity level, particularly pleasant non-drug use social activities, the participant's mood may improve by decreasing avoidance, increasing the potential for social contact, and increasing self-efficacy to engage in such activities. In the final session, the therapist will help the participant identify ways to cope with loneliness-related problems by identifying strategies, evaluating the potential solutions, and selecting a plan to implement the strategies. This discussion will occur in the context of preventing a return to behavioral inactivation and allowing maladaptive thinking to drive poor coping, further maladaptive thinking, and lack of activity.

All participants randomized to CBT-L will be administered the same structured intervention; however, content discussed within the session is tailored based on their within-session responses and beliefs. While different participants may frequently endorse similar beliefs, their ideas about that specific belief may differ. Therefore, the intervention is structured, but not scripted. The same therapist will deliver all 6 sessions.

Physical Health Education Training (PHET; control condition): PHET provides information on the importance and benefits of and guidelines for living a healthy lifestyle. PHET is manualized and contains educational materials on topics such as diet, water consumption, exercise, and sleep. The topics will be delivered across six sessions, which will last ~45 minutes. The same therapist will deliver all 6 sessions. The control condition will help account for nonspecific conditions, such as providing attention or contact by the study interventionist, providing support or building rapport, and managing participants' expectations of treatment outcomes. Importantly, PHET is inert with respect to the outcomes of interest. We selected an active intervention to help maintain engagement. Importantly, both conditions are just 6 weeks, increasing the likelihood of sustaining engagement relative to CBT interventions that are 8-12 weeks. This active intervention also helps decrease the likelihood of participants feeling marginalized, while also providing relevant educational content to facilitate issue-oriented

Page 6 of 20

focus. Supporting the ability of PHET to engage participants, our prior work with PHET indicates that, on average, participants found PHET to be mostly to extremely "easy to understand," found themselves to be "engaged," and "would recommend it to a friend." Training and Supervision

Training for Research Staff: Drs. [name] and [name] will train the project coordinator to administer verbal consent and administer and score the assessment measures through instruction and extensive observed role play. [name] will model the administration of the consent and assessments while the coordinator observes, then they will observe the coordinator administer the consent script and baseline assessment instruments, providing feedback as needed. If more training is required, we will continue to model the interview and/or observe the interview until the coordinator reaches a satisfactory level of skill and comfort. The training will seek to promote reliable, fluid administration of the forms; maintaining a non-threatening, natural manner; accurately recording all responses; and careful checking to ensure that missing data is minimized. The same process will be used for each follow-up assessment session. The coordinator will be blinded to the participants' treatment conditions for the assessments.

Training for Interventionists and adherence rating: Interventionists with at least a master's degree in a counseling/health-related field and prior CBT training will deliver CBT-L and the education control. Drs. [name] and [name] will train the interventionists using the manual. Initial training will consist of lecture and role play "rehearsal" techniques. Ongoing supervision will also be provided throughout the study. No identifying information will be used, noted, or discussed during supervision.

Because each CBT-L session has unique content, we developed session adherence measures that itemize the session-specific content (See **Adherence Checklist Appendix**). Each session will emphasize the completion of worksheets for identifying/changing maladaptive thoughts. Adherence scores will be given for each session and the entire intervention by transforming the total number of points into a percentage of content delivered. Study therapists will track adherence as they complete sessions.

Supervision for Research Team and Interventionists: Weekly meetings will be conducted to focus on monitoring: a) recruitment, b) conducting interviews, c) coding interview data, d) communication between research staff, e) retention; f) completeness of documentation, and g) storing and safeguarding data. To maintain blinding, separate meetings among interventionists and coordinator will occur as needed.

#### Measures

When feasible, well-validated measures available as common data elements will be used. All data collection will be completed by telehealth.

Loneliness: The 20-item Revised UCLA Loneliness Scale will be our primary outcome measure. We will use the 5-item NIH Toolbox Loneliness Scale  as our loneliness screening measure. The NIH Toolbox Loneliness Scale is correlated highly (r = .80) with the Revised UCLA Loneliness Scale.  T-scores >60 indicate loneliness scores 1 standard deviation above the mean and will be used to assess eligibility. 

Opioid-related outcomes. Opioid Use Disorder: The OUD module in the SCID-5-RV will be used to identify an OUD at screening and will be re-assessed at the final follow-up. Opioid use: We will use the Timeline Follow Back (TLFB) from the 60 days prior to baseline through to the end of participation in the study (i.e., 60-day follow-up) to assess days used opioids and percent days abstinent. The TLFB will be completed at each assessment time point so there are shorter intervals facilitating participant recall of their substance use. The TLFB has long-

Page 7 of 20

standing strong psychometric properties and is highly correlated with urine drug screen results, which would be difficult to obtain because there is no in-person contact in the current study. Another advantage of TLFB is that participants may be more honest about their opioid use because there will be no in-person meetings thus increasing relative anonymity and decreasing social desirability/ under-reporting. *Craving: The Penn Craving Scale* (PCS) is a 5-item measure assessing aspects of past-week craving for opioids. Research supports the psychometric properties of the opioid version of the scale. *Consequences of substance use*: The Inventory of Drug

Use Consequences (InDUC-2) will be used to assess drug use consequences in the following domains:

impulse control, social responsibility, physical, intrapersonal and interpersonal. Consequences will be assessed for the last 3 months at baseline and the follow-up will be since the previous assessment.

Social factors. Quality/Quantity of Social Interactions: The Duke Social Support Index-assesses several domains of perceived social support, including social network size, social interaction, social satisfaction, and instrumental social support. Research supports the psychometric properties of the DSSI scales. 77,78 Although all variables will be considered, analysis are focused on the role of the social interaction and social satisfactory scales as measures of quantity and quality of social interactions, respectively.

Table 1. Schedule and content of assessments

| Primary outcome                              |       |
|--|-------|
| Loneliness-NIH Toolbox Loneliness Scale      | S,B,F |
| Loneliness-UCLA Loneliness Scale             | B,I,F |
| Secondary outcome                            |       |
| Opioid use-TLFB                              | B,I,F |
| Mechanistic primary outcomes                 |       |
| Quality/quantity of social interactions-DSSI | B,I,F |
| Negative affect-depression, anxiety PROMIS   | B,I,F |
| Tertiary/exploratory outcomes/mechanisms     |       |
| Burdensomeness/belongingness-INQ-12          | B,F   |
| Craving - PCS                                | B,F   |
| OUD-SCID-5-RV opioid module                  | S,F   |
| Overdose risk behaviors-ORBQ                 | B,F   |
| Drug use consequences-InDUC-2R               | B,F   |
| Key descriptive variables                    |       |
| Possible SUD, substance use-ASSIST, TLFB*    | B,I,F |
| Physical functioning, sleep, pain-PROMIS     | B,F   |
| Profile-29                                   |       |
| Treatment utilization                        | B,F   |
| Demographics                                 | В     |
|  |       |

S-Screening; B-Baseline, I- Intervention; F-Follow-ups/Post; \*only TLFB for mid-intervention assessment

Belongingness: The Interpersonal Needs Questionnaire (INQ-12) assesses thwarted belongingness (i.e., an unmet need to belong) and perceived burdensomeness (i.e., feeling a burden to social support network). This measure will assist in identifying potential cognitive-related mediating pathway between loneliness and opioid use. Research supports the scale's psychometric properties.  We will also explore the quality and quantity of interactions via social media with friends, family, and strangers as there is a mixed results in this area. 

Negative Affect. The depression and anxiety subscales from the PROMIS Profile-29 will be used to assess depression and anxiety. Research supports the psychometric properties of these scales.

Substance Use Disorder Screener. Lifetime and past three-month possible substance use disorder will be assessed using the NIDA-modified Alcohol, Smoking, and Substance Involvement Screening Test (ASSIST). The ASSIST is an 8-item screening measure originally developed by the World Health Organization to assess substance use and problems. The ASSIST asks about both "street" opioids and prescription opioids. Scores ranging from 0-3 suggest lower risk, 4-26 suggest moderate risk, and 27+ suggest high risk. The ASSIST has

Page 8 of 20

strong support for its reliability and validity. We will capture other substance use during the study period using the TLFB.

Physical health and overall functioning. The PROMIS Profile-29 will be used to assess the following domains: physical function, fatigue, sleep disturbance, ability to participate in social roles and activities, and pain interference, in addition to anxiety and depression domains noted above. There is strong support for the measure's psychometric properties.

Overdose Risk Behavior. The Overdose Risk Behavior Questionnaire (ORBQ) assesses the frequency of past-month engagement in behaviors that are associated with overdose. Higher scores on the ORBQ are associated with number of prior overdoses.

Treatment utilization. We will assess participant past and current utilization of pharmacological (e.g., buprenorphine, anti-depressants), psychological, and other supportive interventions (e.g., Narcotics anonymous, CBT) related to substance use and mental health at baseline and follow-up.

COVID questions. This questionnaire was developed to assess if a participant had been diagnosed with the COVID-19, how the disease affected them, if they knew anyone who was diagnoses with COVID-19, and the extent to which the pandemic has affected them across a variety of domains in the last year.

Demographics. At screening, we will assess participants' gender, age, educational background, employment, income, race, ethnicity, marital status, and cohabitation status.

Exit Interview. The exit interview will assess overall impressions and impact of treatment, relationship with the therapist, and ways to improve the treatment (See Appendix). The exit interview will inform future feasibility and acceptability and to further refine the intervention protocol as needed. A modified version of the Abbreviated Acceptability Rating Profile will be used to further assess treatment acceptability.

Perceives Invalidation of Emotion. The Perceived Invalidation of Emotion Scale (PIES) is a 10-item measure assessing the extent to which the respondent perceives that an individual implies that their emotions are incorrect or inappropriate. Research supports the psychometric properties of the measure and construct. 90 The PIES will be administered at the baseline and post-treatment assessments.

Attachment The Revised Adult Attachment Scale-Close Relationship version (AAS) assesses 3 dimensions of adult attachment (close, dependent, anxiety) over 18 items on a 5-point Likert scale (1 – Not at all characteristics of me to 5 – Very characteristic of me). The scale is widely used with strong psychometric properties.91 The AAS will be delivered at baseline and post-treatment assessments.

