# 5. SUBJECT POPULATION

We will nationally recruit 125 adults with OUD for this randomized clinical trial. We estimate that our screen failure rate will be approximately 10-30%. We estimate attrition from the consent and baseline assessment to the end of the 2-month follow-up to be approximately 20%.

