## 9. STUDY PROCEDURES

Screening: The project coordinator will screen by phone following a script. Potential participants will provide verbal consent to complete the screening measures. Those individuals meeting eligibility who are interested in participating will be scheduled for a telehealth-based appointment to go over Consent, complete eConsent, and conduct a baseline assessment. Assessments and Intervention: Participants will be enrolled following consent and will complete the baseline assessment. Following the baseline assessment, participants will be randomized to condition (control or experimental) by a computer-generated algorithm. Participants will schedule a convenient time for their telehealth-based intervention sessions. Mid-treatment, posttreatment, and 30- and 60-day post-treatment follow-up assessments will also be conducted by telehealth. Participants will be paid \$40 each for the baseline and post-treatment assessment, \$20 for the mid-treatment assessment and \$30 each for the 30-day and 60-day follow-up assessments. Participants will also be paid \$20 for completing the first 3 sessions within 4 weeks. The posttreatment assessment will also include an exit interview for participants to describe acceptability of the intervention. All assessments and interventions will be conducted via Zoom (including toll-free phone option) or phone. If requested, participants will be sent a letter indicating study activities completed.

Randomization: We will randomize at the participant level using block randomization in groups of 4. All demographic and outcome variables will be assessed for baseline equivalency. Any between-group baseline differences will be controlled for statistically in all subsequent analyses with baseline differences being defined here as any absolute standardized mean difference (Cohen's d) greater than or equal to .15.

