# 14. PAYMENT FOR PARTICIPATION

Participants will receive compensation for their participation in the study. The compensation amount will be based on the schedule that follows:

| Baseline Assessment                        | \$40 |
|--|------|
| Completing first 3 sessions within 4 weeks | \$20 |
| Mid-intervention assessment                | \$20 |
| Post-treatment Assessment (w/in a week)    | \$40 |
| 30-day Assessment                          | \$30 |
| 60-day Assessment                          | \$30 |

Therefore, the total compensation for completing all the study components would be \$180. Payments will be made following each study procedure listed above. Participants who do not complete the entire study for any reason, will receive compensation for the components that were completed per the above schedule of payments.

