# 15. SUBJECT WITHDRAWALS

- The only anticipated circumstances under which subjects will be withdrawn by the investigator from the research without their consent would be if they were lost to contact and if new information about them suggested that they did not meet eligibility criteria.
- Subjects may withdraw from the research themselves at any time and/or completes some but not all study procedures. We will utilize all data collected.
- If we have not met our target 'n' for study completers, to the extent that funding and staff time allow, we will replace subjects withdrawn from the study.

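### The InDUC recall window is 3 months at baseline but depends on visit dates afterwards, so change over time is confounded with window length

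*Combined protocol and SAP*

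**What the plan says.** The Measures part of Section 9 gives InDUC two different recall rules: "Consequences will be assessed for the last 3 months at baseline and the follow-up will be since the previous assessment".

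Table 1 lists "Drug use consequences-InDUC-2R" among the tertiary/exploratory outcomes, with codes B and F. The key reads "S-Screening; B-Baseline, I- Intervention; F-Follow-ups/Post", so InDUC is due at baseline, post-treatment and both follow-ups, but not mid-treatment.

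The timing comes from other sections:

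- Section 9 has a visit in mid-treatment: "Mid-treatment, posttreatment, and 30- and 60-day post-treatment follow-up assessments will also be conducted by telehealth".
- The Interventions text says "both conditions are just 6 weeks".
- The payment table in Section 14 has "Post-treatment Assessment (w/in a week" as the timing of the post-treatment visit.
- Section 5 estimates attrition from consent and baseline "to the end of the 2-month follow-up to be approximately 20"%.
- The section on subject withdrawals says of people with partial data: "We will utilize all data collected".

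The published text gives no fixed follow-up window for InDUC, no score per unit of time, no offset, no rule for a missed earlier visit and no scoring method. Section 17 names opioid use and craving as the Aim 2 outcomes and does not name InDUC.

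**The concern.** A score that accumulates events over a window depends on how long the window is. Here the baseline window is set by the calendar and each later window by the date of an earlier visit. Three things follow.

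- With full attendance, every follow-up window is shorter than the baseline window, so an apparent improvement can arise with no change in behaviour.
- At post-treatment the starting point is unclear. It could be the last InDUC (baseline) or the last visit of any kind (mid-treatment). Under the second reading, consequences between baseline and mid-treatment are never recorded.
- A participant who misses a visit and then returns reports over a longer window than one who attended, and both stay in the data.

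At stake is the reading of InDUC change over time. The between-arm contrast is also at stake if attendance or pace differs by arm.

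**Working it through.** The documents give no figure for InDUC, so there is nothing to reproduce. The window lengths below are built from the schedule.

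**Inputs from the documents.** Baseline window of 3 months, taken as 90 days. Treatment of 6 weeks, so 42 days. Post-treatment visit within a further 7 days, so day 42-49. Follow-ups 30 and 60 days later.

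**Assumptions.** The mid-treatment visit falls at week 3 (day 21). The 30- and 60-day visits are counted from the post-treatment visit. The consequence rate is constant, meaning no true change. Scoring is by count or any occurrence.

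**Step 1: windows.** Under a constant rate, the expected count relative to baseline is window/90.

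| InDUC score | Situation | Window (days) | Window/90 |
|---|---|---|---|
| Post-treatment | counted from baseline | 42-49 | 0.47-0.54 |
| Post-treatment | counted from mid-treatment | 21-28 | 0.23-0.31 |
| 30-day or 60-day | preceding visit attended | 30 | 0.33 |
| 60-day | 30-day visit missed | 30 + 30 = 60 | 0.67 |
| 30-day | post-treatment missed, counted from baseline | 42 + 30 = 72 | 0.80 |
| 30-day | post-treatment missed, counted from mid-treatment | 21 + 30 = 51 | 0.57 |
| 60-day | post-treatment and 30-day missed, counted from baseline | 42 + 60 = 102 to 49 + 60 = 109 | 1.13-1.21 |

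**Step 2: any-occurrence scoring.** If p is the chance of endorsing an item over 30 days, the chance over d days is 1 - (1 - p)^(d/30). The values of p are assumed.

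- p = 0.2: 0.20 at 30 days, 0.36 at 60 and 0.49 at 90. The fall from 90 to 30 days is 1 - 0.20/0.488 = 59%.
- p = 0.3: 0.30, 0.51 and 0.66. The fall is 1 - 0.30/0.657 = 54%.
- Over a wider range, a 90-day probability of 0.10 falls by 65% and one of 0.95 falls by 34%.

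**Step 3: unequal attendance between arms.** Suppose a fraction m of those seen at 60 days missed the 30-day visit, and that missing is unrelated to consequences. Endorsement at 60 days is then (1 - m) × (30-day chance) + m × (60-day chance). With assumed m of 10% in one arm and 25% in the other:

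- p = 0.2: 0.90 × 0.20 + 0.10 × 0.36 = 0.216, against 0.75 × 0.20 + 0.25 × 0.36 = 0.240. The difference is 2.4 points.
- p = 0.3: 0.90 × 0.30 + 0.10 × 0.51 = 0.321, against 0.75 × 0.30 + 0.25 × 0.51 = 0.353. The difference is 3.2 points.

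If m is the same in both arms, the difference is zero.

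**Step 4: other measures in the plan.** The overdose-risk questionnaire uses a fixed past-month window, the craving scale a past-week window, and the Timeline Follow Back yields a percentage of days. None of these has InDUC's problem.

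**The case against.** **The trial tests a difference between arms.** The Aim 1 and Aim 2 hypotheses are comparisons with the education control, and the Aim 1 model in Section 17 includes time by condition. Both arms follow the same schedule. With no true effect and similar attendance and pace, the window change produces no expected difference between arms. This stands. A reader might infer that the randomised InDUC comparison is biased as planned, but the documents give no reason to expect attendance to differ by arm. The number and length of sessions match, and the control was chosen partly to keep people engaged. Equal pace is still an assumption: the plan pays for completing three sessions within four weeks although CBT-L sessions are weekly, so some slippage is foreseen.

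**The bias illustration uses assumed rates.** The documents give about 20% overall attrition and no rate of missing one visit and then returning. People who leave for good contribute no long-window score. The size is also modest. With 125 × 0.8 = 100 completers, about 50 per arm, the standard error of the Step 3 differences is √[(0.216 × 0.784 + 0.240 × 0.760)/50] = 8.4 points, and 9.4 points for the second pair. This stands too.

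**The drop depends on scoring.** If items ask for average frequency within the window, the fall would be smaller or absent. A reader might infer that scores must drop, but without stated scoring that is conditional.

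**Not every missed visit doubles the window.** A reader might generalise from the missed 30-day visit. Missing post-treatment instead gives 72/30 = 2.4 or 51/30 = 1.7 times the usual 30-day window. Missing both visits can exceed the baseline window, which reverses the direction of the artefact.

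**Asking back to the last visit has merit.** It gives continuous coverage without overlap. This holds if the starting point is the last InDUC, but not if it is the mid-treatment visit.

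**Conclusion.** The concern holds as a minor point. The windows differ by rule, the starting point at post-treatment is undefined, and the published text neither fixes the window nor adjusts for it. Within-arm change and the time effect for InDUC are confounded with window length. Under count or any-occurrence scoring and a constant rate, the artefact from a 90-day to a 30-day window is a two-thirds fall in expected count, or a 54-59% fall in endorsement at an assumed 30-day probability of 0.2-0.3.

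The between-arm contrast gains noise. It is biased only if missed visits or session pace differ by arm, by 2.4-3.2 points on an item in the assumed 25% versus 10% case.

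A reader might conclude that InDUC results are uninterpretable. The documents do not support that: a comparison between arms at a given visit remains usable if attendance is similar. InDUC is tertiary/exploratory and absent from the analysis plan, and the primary loneliness result is unaffected.

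**What to change.** Use one InDUC recall window of the same length at baseline and at every follow-up, independent of the date of the last visit. This is a wording change on the form. A short window captures fewer rare events at baseline and leaves some days unobserved. With 30 days, that is 42 - 30 = 12 to 49 - 30 = 19 days before post-treatment, and a whole month when the 30-day visit is missed.

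If continuous coverage is preferred, define the starting point as the last InDUC, record the start and end dates of each window, and analyse a rate or include window length as an offset or covariate. This keeps all the days, but an offset assumes that scores rise in proportion to time. A covariate would be hard to separate from visit, because the 90-day window occurs mainly at baseline.

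In either case, state how items are scored, and reconcile the instrument label, which is InDUC-2 in the Measures text and InDUC-2R in Table 1.
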